6.5. Blinding

The OXYPuF trial is an open label trial.

6.6. Informing the participant's GP and other parties

In order to be randomised into the OXYPuF trial, the participant must agree to their GP being contacted. The participant's GP should be notified that they are in OXYPuF trial, using the **OXYPuF GP Letter**.

7. TRIAL INTERVENTION

7.1. Name and description of investigational medicinal product

IMP	Name of IMP	Formulation
Medical Oxygen	Medical Oxygen, 100% inhalation gas	Oxygen Ph Eur 100%v/v (no other ingredients)

7.2. Trial intervention(s) and dosing schedule

The intervention is defined as oxygen used during physical activity, delivered by cylinders or concentrator, via either face mask or nasal cannulae, at a flow maintaining saturations >90%. Patients will be provided with instructions on how to use the oxygen cylinders/concentrators and informed that they will need to use the oxygen when they feel breathless. This can be different for each patient.

7.3. Drug interaction or contraindications

There are no relevant interactions. All patients contraindicated for oxygen are not eligible for the trial.

7.4. Accountability Procedures

For patients randomised to the oxygen arm, oxygen use will be estimated in two ways..

7.5. Intervention modification or discontinuation

It is the nature of AOT that its use will be self-administered as required. There are no obvious clinical reasons for modifying the availability of oxygen to those allocated to the AOT arm.

7.6. Continuation of intervention after the trial

Since provision of AOT is a commonly used therapy, there would be no issue with a patient on the AOT arm continuing after the trial ends based on the opinion of the local investigator as to whether they have benefitted from it.

Similarly, patients on the breathlessness advice arm could be provided with AOT after the trial ends based on the opinion of the local investigator as to whether they have benefitted from it..

7.7. Intervention supply and storage

7.7.1. Intervention supplies

Local HOSAR (home O2 assessment and review services) will provide oxygen according to normal NHS practice to those patients randomised to the AOT group.

7.7.2. Packaging and labelling

Routine stock will be used and no additional labelling will be required in accordance with the Risk Adapted Approaches to the Management of Clinical Trials of Investigational Medicinal Product guidance regarding Type A trials for products with an MA, where the product is being used within the terms of its MA and the prescription for its use.

7.7.3. Drug storage

In the context of an IMP, oxygen cylinders can be stored at ambient temperature for longer than 6 months (the duration of the trial).

Oxygen concentrators are designed to operate at ambient temperatures. Cylinders which are partially full at the end of an individual's participation in the trial can be continued to be used if, in the opinion of the clinician, the participant would benefit from continuing AOT. Otherwise such cylinders will be returned to the supplier.

7.8. Accountability

The provision of oxygen cylinders to those patients randomised to the AOT arm will be via the normal routes (i.e. from the hospital oxygen service directly to the patient's homes). Re-provision is the responsibility of the patient and hospital oxygen service.

7.9. Adherence

Adherence will be monitored via collecting the number and type of oxygen cylinders a patient is using per week. This information will be self-reported by the patient and included on the baseline and follow up forms.

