8.1.3 Progression Criteria for internal pilot to main trial

Progression criteria are based on recruitment and data received.

Recruitment rate. If sites, overall, recruit 2 patients per month, and each site has a target of ~17 patients; each site will complete recruitment in 11 months; this represents green as recruitment would be completed by 18 months, assuming a steady rate of sites opening. If overall recruitment was 0.5-1.9 patients/centre/month, we would amend recruitment methods as described above, and if there were <0.5 patients/centre/month this represents red (stop).

Critical data receipt. We do not anticipate issues with data collection, since the primary outcome is a questionnaire collected directly from patients. If ≥90% of critical data is received for patients this would be considered green, 80-89%=amber and ≤79% =red. Critical data refers to primary and safety data.

The progression criteria are summarised in the table 1 below:

Table 1 Progression Criteria

	Green (go)	Amber	Red (stop)
Recruitment rate average patients per site per month	≥1.9	0.5 to <1.9	<0.5
Acceptability	High	Low	Low
Non-adherence	≤20%	21-29%	≥30%
Critical data receipt	≥90%	80-89%	≤79%

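### The pilot's non-adherence stop row is undefined, and the cylinder count in section 7.9 gives no adherence data for participants supplied by concentrator

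*Protocol*

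**What the plan says.** Protocol section 8.1.3, Table 1, has a row reading "Non-adherence ≤20% 21-29% ≥30" (per cent), with the columns go, amber and stop. The text above the table says "Progression criteria are based on recruitment and data received" and explains only those two rows. It does not say what counts as non-adherence, what the percentage is a percentage of, or which contact supplies it.

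Section 7.9 gives the measure: "Adherence will be monitored via collecting the number and type of oxygen cylinders a patient is using per week". It adds: "This information will be self-reported by the patient and included on the baseline and follow up forms".

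Section 7.2 describes what is being adhered to: "The intervention is defined as oxygen used during physical activity, delivered by cylinders or concentrator". Participants are "informed that they will need to use the oxygen when they feel breathless. This can be different for each patient". Section 7.5 adds: "It is the nature of AOT that its use will be self-administered as required".

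Two other places bear on oxygen use. Section 7.4 says that "oxygen use will be estimated in two ways", and the text ends there. A fidelity call to the AOT arm is set at one week in section 6.3 and at three weeks in section 9 and Table 2. Section 9 explains that oxygen may take two to three weeks to arrive. No question about oxygen use is stated for the call.

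**The concern.** A progression criterion needs a definition and data that can satisfy it. Here the definition is absent, and the one measure specified covers one of the two permitted devices. A definition can be written later. A use record for concentrator participants cannot be created later if the forms did not ask for it.

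What is at stake is the pilot decision on this row, and the trial's description of adherence more widely. Section 1.2 warns that compliance with ambulatory oxygen may be low and gives assessment of adherence as a reason for a pragmatic trial.

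**Working it through.** **Is there a figure to reproduce?** The 20% and 30% cut-offs have no derivation in the protocol. The sample size in section 15.1 does reproduce: a difference of 4.0, SD 8.85, 90% power and two-sided 5% give 103.84, so 104 per group by the t-test; 208 / 0.8 = 260. Adherence does not enter that calculation, and section 15.2 analyses participants as randomised whatever their adherence. Neither is touched by this point.

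**Cylinder users.** Use is as required, so there is no expected weekly count. A rule of any use versus none needs no expected count and could be applied to the section 7.9 data. The protocol does not state that rule, and the choice matters. As an illustration only, assume weekly cylinder use is Poisson with mean 2 and call a participant non-adherent below a cut-off:

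- fewer than 1 cylinder: e^-2 = 13.5% (go)
- fewer than 2: 3e^-2 = 40.6% (stop)
- fewer than 3: 5e^-2 = 67.7% (stop)

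The row can be evaluated for cylinder users once a rule is fixed.

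**Concentrator users.** A participant supplied only by concentrator has no cylinders to count, so the section 7.9 data cannot separate use from non-use under any rule.

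**What that does to the arm-level percentage.** Let c be the share of the AOT arm supplied only by concentrator and p the non-adherence among cylinder users. The protocol gives neither, so both are assumptions. With nothing known about the concentrator users, arm-level non-adherence lies between

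- lower bound, all of them adherent: (1 - c)p
- upper bound, none of them adherent: c + (1 - c)p

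The width is c.

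| c | p = 5% | p = 10% | p = 15% |
|---|---|---|---|
| 10% | 4.5% to 14.5% | 9% to 19% | 13.5% to 23.5% |
| 20% | 4% to 24% | 8% to 28% | 12% to 32% |
| 30% | 3.5% to 33.5% | 7% to 37% | 10.5% to 40.5% |

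The upper bound passes 20% when c exceeds (0.20 - p)/(1 - p): 15.8%, 11.1% and 5.9% for p = 5%, 10% and 15%. It reaches 30% at c = (0.30 - p)/(1 - p): 26.3%, 22.2% and 17.6%. Below the first value the gap cannot move the row out of go; above the second, the same data are compatible with go and with stop. The upper bound is also the figure that would be reported if blank cylinder counts were read as no use.

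**Can another stated item fill the gap?** Section 7.4 names no method. The fidelity call has no stated content on use. Baseline forms precede the supply of trial oxygen. Nothing else in the protocol specifies concentrator use.

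**The case against.** A reader might infer that the whole row cannot be evaluated, because as-required oxygen has no expected amount. The documents do not support that. An any-use rule needs no expected amount, and for cylinder users a count of zero versus more than zero comes close to supplying it. Choosing the cut-off could be left to an analysis plan.

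A reader might also infer that concentrator use will never be collected. That is too strong. Section 7.4 intends a second method. The call could carry a question on use, the 3-month visit reviews the prescription, section 16.2 costs the oxygen within the trial, and the form list in section 12.2 is not exhaustive. None of these states a measure of concentrator use, so what can be said is that none is specified.

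A third inference is that adherence data would arrive too late for a six-month pilot, because the 3-month form is the first to carry them. This depends on when the pilot clock starts, which is not stated, and on the 3-week call not counting as a follow-up form, although section 9 calls it a follow-up.

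The size is also open to challenge. Sections 3.2 and 7.8 describe supply in terms of cylinders, so c may be small. Section 12.2 has blank fields queried, so reading a concentrator user's blank as no use is unlikely. The more realistic outcome is a percentage that describes cylinder users only. These points limit the consequence; they do not supply the missing definition or the missing device.

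**Conclusion.** The point holds in a limited form. Table 1 sets a stop level for a quantity the protocol does not define, and the only specified measure omits a delivery device that section 7.2 permits. As written, the row can describe cylinder users at best, under an unstated rule. For concentrator users section 7.9 provides no adherence data, and a later analysis plan could not recover them.

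The size is unknown because the concentrator share is not given; the table above shows assumed values only. A reader might infer that the trial could be stopped wrongly, but the protocol does not say that a red row stops the trial automatically, and section 18.4 gives oversight of progress to the steering committee. The effect is confined to the pilot's non-adherence row and the reporting of adherence. It should be corrected because the correction is cheap and cannot be made after the data are in.

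**What to change.** 1. In section 7.9, record device type and concentrator use in hours per week alongside cylinders.
2. Add one question on oxygen use in the past week when breathless on activity, covering either device, with answers such as always, sometimes, never and not breathless. Put it on the existing 3-week call and on the 3- and 6-month forms. Do not use the one-week timing in section 6.3, because the oxygen may not yet have been delivered.
3. Under Table 1, define non-adherence as the percentage of participants randomised to AOT and due the 3-week call who, at their latest contact, had declined or stopped oxygen or reported never using it when breathless on activity. Keep in the denominator those who stopped oxygen and then withdrew; removing them would understate non-adherence. Report not breathless, supply delay and non-response separately.
4. Complete section 7.4 by naming both methods or referring to section 7.9.

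Leave the intervention definition in sections 1.2.3 and 7.2 as it is. Tying it to breathlessness would narrow it and could leave out people who desaturate without feeling breathless.

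The cost is protocol wording, one extra question and one extra field, with no added visits or participants. The measure remains self-reported and relies on one-week recall.

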8. OUTCOME MEASURES

8.1. Internal pilot outcomes

8.1.1. Recruitment rate

The aim is to open 50% of sites by 6 months from study approval by the relevant authorities, and target an overall recruitment rate of 2 patients per site per month. If recruitment is sub-optimal, we will consider increasing the number of sites, enrolling other forms of pulmonary fibrosis (e.g. fibrotic non-specific interstitial pneumonitis (NSIP)), and enrolling a greater proportion of non-desaturating patients. We will not include connective tissue disease associated ILD as these patients may have other co-morbidities or functional deficits (e.g. mobility issues from joint disease), and this could influence outcomes. We will also examine reasons for non-inclusion of patients in the study; if high rates of identification occur, but patients decline screening, this implies the trial may not be possible

to complete, and such data would be interpreted alongside the acceptability analysis to determine if the study should continue.

8.1.2 Acceptability of intervention

To provide a description of the data, including different dimensions of acceptability and drawing out any differences (e.g. if some groups find it acceptable and others don't).

8.1.3 Progression Criteria for internal pilot to main trial

Progression criteria are based on recruitment and data received.

Recruitment rate. If sites, overall, recruit 2 patients per month, and each site has a target of ~17 patients; each site will complete recruitment in 11 months; this represents green as recruitment would be completed by 18 months, assuming a steady rate of sites opening. If overall recruitment was 0.5-1.9 patients/centre/month, we would amend recruitment methods as described above, and if there were <0.5 patients/centre/month this represents red (stop).

Critical data receipt. We do not anticipate issues with data collection, since the primary outcome is a questionnaire collected directly from patients. If ≥90% of critical data is received for patients this would be considered green, 80-89%=amber and ≤79% =red. Critical data refers to primary and safety data.

The progression criteria are summarised in the table 1 below:

Table 1 Progression Criteria

	Green (go)	Amber	Red (stop)
Recruitment rate average patients per site per month	≥1.9	0.5 to <1.9	<0.5
Acceptability	High	Low	Low
Non-adherence	≤20%	21-29%	≥30%
Critical data receipt	≥90%	80-89%	≤79%

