2. AIMS AND OBJECTIVES

2.1. Internal pilot objectives

The pilot phase of the trial will last 6 months and afford the opportunity to assess both recruitment rate and conduct a qualitative study to explore the acceptability of the trial intervention.

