3.2. Trial setting

The study is set in secondary care, enrolling participants from approximately 20 hospital outpatient clinics or community oxygen services with the trial intervention used by patients in their own homes. For the treatment arm, oxygen cylinders will be delivered to the participant's home for use in their day-to-day life, hence whilst initial assessment is in secondary care, treatment is received in the community.

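### The pilot progression rules in Protocol 8.1.3 and Table 1 contain a wrong recruitment calculation, conflicting limits at 1.9, one acceptability result under two actions, and a primary-outcome check that falls due after the pilot

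*Protocol*

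**What the plan says.** Protocol 8.1.3 sets the go, amend and stop rules for the internal pilot, which Table 1 summarises.

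- **Recruitment.** The green case starts from "If sites, overall, recruit 2 patients per month" and continues "each site has a target of ~17 patients; each site will complete recruitment in 11 months". It concludes that "recruitment would be completed by 18 months, assuming a steady rate of sites opening". The text grades 0.5 to 1.9 per centre per month as amber and below 0.5 as red. Table 1 makes 1.9 or more green, 0.5 to under 1.9 amber and below 0.5 red.
- **Number of sites and trial size.** Section 3.2 describes "enrolling participants from approximately 20 hospital outpatient clinics or community oxygen services". Section 15.1 sets the total at 260. Sections 2.1.1 and 8.1.1 aim for half the sites to be open 6 months after approval.
- **Acceptability.** Table 1 lists High for green, Low for amber and Low for red.
- **Critical data.** Receipt of 90% or more is green, 80-89% amber and 79% or less red. "Critical data refers to primary and safety data".
- **Timing.** Section 2.1: "The pilot phase of the trial will last 6 months". Section 8.2.1 makes the primary outcome the K-BILD total score at 6 months after randomisation. Table 2 collects K-BILD at baseline and 6 months only.

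**The concern.** These rules decide whether the trial continues, is amended or stops, so they should give one answer for any pilot result and rest on figures that agree with the rest of the protocol.

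The site-level calculation offered in support of green is arithmetically wrong, and its per-site target does not fit the stated number of sites. The text and the table disagree at one of the limits. One acceptability grade leads to two different actions. The data-receipt rule depends partly on an outcome that is not yet due when the decision is made. Whoever applies the rules would have to settle these points after seeing the pilot results, which is what progression criteria set in advance are meant to prevent.

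**Working it through.** **1. Time per site.** Inputs from 8.1.3: rate 2 per site per month, target about 17, stated duration 11 months.

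- Duration = target / rate = 17 / 2 = 8.5 months. The stated 11 is not reproduced.
- Reading about 17 as 16.5 to 17.4 gives 8.25 to 8.7 months. Using 1.9 per month instead of 2 gives 17 / 1.9 = 8.9 months (8.7 to 9.2 over the same range). No variant reaches 11.
- Working back: 11 × 2 = 22 patients, and 17 / 11 = 1.55 per month. The second is amber under both text and table, although it is offered as the green case.

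**2. Target per site.** Inputs: 260 patients (15.1), about 20 sites (3.2).

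- 260 / 20 = 13 per site, and 13 / 2 = 6.5 months.
- 17 × 20 = 340, not 260. A target of 17 fits 260 / 17 = 15.3 sites.
- The total itself is sound: 104 per group gives 208, and 208 / 0.8 = 260.

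**3. Recruitment limits side by side.**

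| Rate per site per month | Text of 8.1.3 | Table 1 |
|---|---|---|
| exactly 1.9 | amber | green |
| between 1.9 and 2 | no band stated | green |
| 2 | green | green |

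**4. Calibration against 18 months.** Assumptions: S sites open evenly over 12 months (extending half by month 6), the 18 months start when the first site opens, and sites keep recruiting until the trial total is met.

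- Site-months by month 18 = S × 12 / 2 + S × 6 = 12S.
- S = 20: 240 site-months, required rate 260 / 240 = 1.08.
- S = 15: 180 site-months, required rate 260 / 180 = 1.44.
- With all sites open sooner, by month 7 or 9, the required rate falls to 0.90 or 0.96 (20 sites) and 1.20 or 1.28 (15 sites).
- At 2 per month with 20 sites, month 12 gives 120 × 2 = 240 patients. The last 20 arrive at 40 per month, so 260 is reached at 12.5 months. With 15 sites it is 12 + (260 − 180) / 30 = 14.7 months.

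Taking the 11 months at face value, an 18-month finish needs the last site open by month 18 − 11 = 7, when the plan has only half of them open at month 6.

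**5. Data due within the pilot.** Assumption: 10 sites open evenly over the 6 pilot months, each recruiting 2 per month.

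- Randomised by month 6: (10 × 6 / 2) × 2 = 60.
- Past 3 months' follow-up: (5 × 3 / 2) × 2 = 15.
- Past 6 months' follow-up: 0.

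Even with all 10 sites open on day 0, 10 × 2 × 6 = 120 would be randomised and 10 × 2 × 3 = 60 would have reached 3 months. Only someone randomised on the first day could have a 6-month K-BILD due. No K-BILD is collected at 3 months.

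**6. Acceptability.** Low is the entry for both amber and red. Section 8.1.2 promises a description of acceptability and gives no grading that would separate the two.

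**The case against.** A reader might infer that the rules cannot be applied at all. That goes too far. The recruitment bands are numeric and can be computed; the wrong 11 months damages their justification, and the direct conflict is confined to rates from 1.9 to just under 2. The critical-data rule can be read as meaning data due, and safety data do fall due during the pilot. The protocol does not say so, however, and the primary-outcome part stays empty on either reading.

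Acceptability is not meant to be read alone. Section 3.3.1 links negative attitudes together with poor recruitment to a discussion with the funder, and 8.1.1 reads refusals alongside the acceptability work. Low might therefore be amber or red depending on recruitment, but Table 1 does not say this. A cell label lost in extracting the table from PDF cannot be ruled out.

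The calibration depends on assumptions. Sites are only approximately 20, the opening pattern after month 6 is not given, and sites are assumed to recruit beyond their own target. If each stopped at its target and the last opened at month 12, completion at 2 per month would be at 12 + 6.5 = 18.5 months with 13 each, or 12 + 8.5 = 20.5 with 17 each. Neither rescues the published chain of 17 patients, 11 months and 18 months, but this is a reason not to put particular new limits forward here.

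Three stronger inferences are not supported:

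- *Amber would dilute the population.* Amber leads to amended recruitment methods. Section 8.1.1 lists options to be considered, and adding sites is the first. Another is "and enrolling a greater proportion of non-desaturating patients", but such patients are already eligible, since 4.1 has no desaturation criterion.
- *The 0.5 limit lets a hopeless trial continue.* Rates of 0.5 and just above are amber, which calls for amendment. A projection of failure assumes that no remedy is applied.
- *Non-adherence is undecidable.* Section 7.4 refers to two ways of estimating oxygen use, although its text then stops, and a detailed definition may sit in the SAP. What stands is narrow: 7.9 says "Adherence will be monitored via collecting the number and type of oxygen cylinders a patient is using per week", while 7.2 also allows concentrators.

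**Conclusion.** The point holds as a set of correctable errors in 8.1.3 and Table 1, and should be fixed before the pilot decision. Four parts rest on the protocol's own words and need no modelling:

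- 8.5 months against a stated 11, with 13 per site (about 20 sites) against a stated 17 (about 15 sites);
- opposite gradings at exactly 1.9, and no text band between 1.9 and 2;
- one acceptability grade under two actions;
- a stop rule at 79% or less with no usable primary-outcome denominator within the pilot.

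The calibration result is conditional. With evenly opening sites and no cap per site, the rate needed for 260 by month 18 is about 1.08 with 20 sites and 1.44 with 15. Both lie well inside amber, so the stated 18-month reasoning does not support a green limit of 1.9. It does not establish what the limit should be.

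The sample size of 260 and the primary analysis are unaffected.

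**What to change.** Edit 8.1.3 and Table 1:

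1. State a per-site target and duration that agree with 260 patients, the planned number of sites and the assumed rate (for 20 sites at 2 per month, 13 patients and 6.5 months).
2. Use identical recruitment limits in text and table, with no gap. Re-derive them from the rate needed to reach 260 in 18 months under a stated site-opening plan, saying whether sites may exceed their own target.
3. Give amber and red acceptability distinct entries, for example mixed and low, or define red as low acceptability combined with the recruitment result, in line with 3.3.1.
4. Define critical data receipt as the percentage received of data due by the decision date, covering safety and 3-month data. Check 6-month K-BILD return later, once pilot participants reach that visit. Baseline K-BILD is a poor substitute: 6.3 requires the baseline booklet before randomisation, so (assuming K-BILD is in that booklet) its completion would be near 100% by design.
5. Reconcile 7.9 with 7.2 so that the adherence record covers concentrators as well as cylinders.

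The cost is a text amendment agreed with the funder and the Trial Steering Committee, plus one later check of K-BILD return. No extra patients or visits are needed.
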